5.4 Follow-Up Procedures and Therapy Transitions

There are no follow-up procedures or therapy transitions. Subjects receiving botulinum toxin will be allowed to continue with injections as they desire.

5.5 Study Timetable / Schedule of Events

Pre-screening of all participants will be completed by phone, email or in person. Onsite testing will include answering to study questionnaires, voice quality assessments, completing TMS tests, and the rTMS protocol. Testing will occur prior to botulinum toxin injection for those patients with AdSD currently being treated with the toxin. Data will be collect when symptoms are at their worst according to the patient's self-report. However, due to the demanding time commitment placed on participants, flexibility will be allowed to modify the schedule if needed. Botulinum toxin injections will be administered by each participant's physician and the costs associated with injection will not be covered by the study.

Experiment schedule		
Pre-screening	Study visit	
Review consent form	Consent and HIPAA	
Medical history	On-site screening	
Eligibility	Report of symptoms	
	Clinical assessment, voice quality and disability	
	Corticospinal excitability (TMS pre-tests)	
	20 min of rTMS	
	Voice quality assessment	
	Corticospinal excitability (TMS post-tests)	
	Report of symptoms	

5.6 Study Protocol Compliance / Treatment Adherence

Subjects will be notified of the voluntary nature of participation. In the consent forms, subjects are made aware of the resources for those who wish to withdraw from the study. Criteria and procedures for withdrawing subjects are noncompliance and disqualification by previously outlined criteria, such as a developed neurological disease, implanted device, or pregnancy. See section 5.8 for more detail. Refer to section 5.8 for subject withdrawal and replacement.

5.7 Deviations from the Clinical Protocol

When a deviation from the protocol is necessary for an individual subject, the investigator will complete a description of the deviation from the protocol and justification on the Protocol Deviation Form.

5.8 Subject Withdrawal

5.8.1 How to Withdraw Subjects

Subjects may be withdrawn from the study for the following reasons:

- o occurrence of intolerable pain or discomfort during testing
- o failure to attend scheduled testing or treatment sessions
- o subject consent withdrawal

In the event of subject withdrawal, all collected data and personal information will be documented and kept private. If a subject is withdrawn from the study, they will keep their identifier code and an additional subject will be recruited to account for the needed subject sample. Withdrawn subjects will be documented and future participants will start at the beginning of the study. Additional subjects will be drawn from the same pool of candidates who expressed interest in the study. The same recruitment procedures and experimental procedures will be followed for all subjects.

5.8.2 Data Collection and Follow Up for Withdrawn Subjects

For withdrawn subjects, documentation will be made. If a subject withdraws before consenting to the study, screening information will be documented and reported.

Withdrawal will be determined from a volunteer's personal decline on-site in which case no calls or letters will need to be used.

5.9 Subject Compensation

Subjects will receive a \$100 gift card to compensate for their participation in the study.

6.0 Data Collection and Analysis

6.1 Subject Population(s) for Analysis

All subjects will have corticospinal excitability and voice quality measurements taken before and after rTMS. All subject data will be processed and analyzed to explore for the effects of rTMS. Self-reported voice disability will be measured before TMS testing in participants with AdSD.

6.2 Statistical Methods

For both groups, changes from baseline will be explored for effects of rTMS in corticospinal excitability and voice quality. Since this is a pilot study and the sample size will likely not be adequate for differential statistics, data will be analyzed with descriptive statistics (measures of central tendency and variability) to look for trends related to rTMS effects and group.

7.0 Safety and Adverse Events

7.1 Definitions

Adverse Event (AE)

An adverse event (AE) is any symptom, sign, illness or experience that develops or worsens in severity during the course of the study. Intercurrent illnesses or injuries will be regarded as adverse events. Abnormal results of laboratory or diagnostic procedures are considered to be adverse events if the abnormality:

- Results in study withdrawal
- Is associated with a serious adverse event
- Is associated with clinical signs or symptoms
- Leads to additional treatment or to further diagnostic tests
- Is considered by the Investigator to be of clinical significance.

Serious Adverse Event (SAE)

A serious adverse event (SAE) is any adverse event that is:

- Fata
- Life-threatening
- Requires or prolongs a hospital stay
- Results in persistent or significant disability or incapacity
- A congenital anomaly or birth defect

Important medical events are events that may not be immediately life-threatening, but are clearly of major clinical significance and may be SAEs.

They may jeopardize the subject, and may require intervention to prevent one or the other serious outcomes noted above.

Hospitalization

Hospitalization shall include any initial admission (even if less than 24 hours) to a healthcare facility as a result of a precipitating clinical adverse effect; to include transfer within the hospital to an intensive care unit. Hospitalization or prolongation of hospitalization in the absence of a precipitating, clinical adverse effect (e.g., for a preexisting condition not associated with a new adverse effect or with a worsening of the preexisting condition; admission for a protocol-specified procedure) is not, in itself, a serious adverse effect.

Unanticipated Adverse Device Effect (UADE)

An unanticipated adverse device effect is any serious adverse effect on health or safety or any life-threatening problem or death caused by, or associated with, a device, if that effect problem, or death was not previously identified in nature, severity, or degree of incidence in the investigational plan, or any other unanticipated serious problem associated with a device that relates to the rights, safety, or welfare of subjects.

Unanticipated Problems Involving Risk To Subjects or Others (UPIRTSO)

An adverse event that in the opinion of the Principal Investigator is unexpected, related to the device, and serious.

7.2 Safety Monitoring Plan

Plans to minimize risks to study participants:

- All investigators and study staff have completed required training re: human subject protections. Study staff will comply with all related regulations and laws, included, but not limited to 45CFR parts 60 and 64, and HIPAA Privacy Regulations.
- Subjects will be rigorously screened against inclusion/exclusion criteria to ensure that their participation is safe.
- Research staff conducting clinical research procedures will be appropriately trained, licensed, credentialed and supervised
- PI and study staff will monitor incidence of adverse events, feedback from subjects, observations from nurses, study staff, investigators and other safety indicators on a continuous basis.
- To monitor symptoms or changes in health status due to TMS testing and rTMS delivery, participants will be asked to complete the form "Subject Report of Symptoms" before TMS testing, right after rTMS application, and at the end of the experiment so that the required actions are taken.
- Study visits will be conducted at the CTSI Masonic Clinical Research Unit (MCRU) or Delaware Clinical Research Unit (DCRU) which are staffed with back-up personnel and have immediate access to Fairview's emergency response personnel if needed.

- PI will ensure accuracy, completeness, clarity and timeliness of all study records.
- Study data & information will be kept confidential and managed in accordance with requirements of HIPAA. All data will be stored in locked offices and not released without subject permission.
- Subjects may discontinue participation at any time, for any reason. Any subject observed to have unacceptable responses to research procedures, or to be unable to safely tolerate participation in the study will be withdrawn.

7.2.1 Anticipated Risks / Risk Mitigation

- 1. Personal information: There is a small risk of loss of confidentiality. Subjects will be asked if they have any medical conditions and if they are taking any medications. This is important to know so that only those subjects who meet the inclusion and exclusion criteria are accepted into the study. A number of procedures are in place to protect participant confidentiality. Every participant enrolled in the study will receive a unique code number. All records and results will be labeled with this code number and the code will be shared only with the study investigators. Any information that is included in published manuscripts (e.g. demographic information) will not be linked to any other information that would identify who the subject was.
- 2. TMS: Risks associated with TMS are rare but should be recognized and prevented with appropriate precautions. Serious adverse risks include the induction of a seizure. There have been reports of a seizure and induced mania from rTMS but none of these side effects have been reported with the type of rTMS that we are doing in this study. Mild adverse effects include fainting, headache, dental pain, and other changes in memory, mood, and hearing. The overall occurrence of a mild adverse event is 5% in sham and real TMS sessions combined (Maizey et al., 2013). Participants will be asked to complete the form "Subject Report of Symptoms" before TMS testing and at the end of the experiment so that the required actions are taken in case there are any changes to their health status. Participants will be instructed to contact study staff if they noticed any of the symptoms listed above after participation in the study. In addition, study staff may contact participants (via email or phone call) to follow-up on any issues or symptoms that occur during the experiment. People with a history of seizure within the last two years or a history of bipolar disorder will not be allowed to participate in this study. The tests may be discontinued without the participant's consent if the study team observes any abnormal responses. TMS delivery may also interfere with implanted devices and, thus, TMS is not appropriate for persons with medical devices such as deep brain stimulators, pace makers and medication pumps. Currently, the effects of TMS on hormonal cycles and the unborn fetus are unknown.
- 3. Needle (fine-wire) electrodes: Risks associated with the electrode placement are very rare and include vocal cord hemorrhage, hoarseness of voice, infection, or dysphagia (difficulty swallowing). Participants should not be on any blood thinner medication to avoid vocal cord hemorrhage. We will clean and prepare the skin

appropriately prior to using needle EMG to avoid infections. Subjects may experience localized minor discomfort in the area during the procedure and for 1-2 days afterwards.

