4.0 Study Design

4.1 Overview of Study Design

This experiment is a pilot study involving within and between group comparisons: AdSD compared to healthy controls, before and after rTMS delivery. Participants will be asked to come to the University of Minnesota for 1 session.

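### The symptom form is due three times in section 7.2 but twice in 7.2.1 and 5.5, no form falls just before rTMS, and adverse events after the visit are captured only passively

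*Combined protocol and SAP*

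**What the plan says.** Safety and feasibility form Aim 1 (section 3.1). The hypothesis is judged by the absence of serious adverse events and by every participant completing the study. The study is a single visit: "Participants will be asked to come to the University of Minnesota for 1 session" (section 4.1).

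Three places set the timing of the Subject Report of Symptoms:

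- Section 7.2: "before TMS testing, right after rTMS application, and at the end of the experiment so that the required actions are taken".
- Section 7.2.1, item 2: "before TMS testing and at the end of the experiment so that the required actions are taken in case there are any changes".
- Section 5.5: the row "Report of symptoms" appears twice, once after on-site screening and once as the last row. Nothing of the kind stands between rTMS and the voice assessment that follows it.

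On the time after the visit, section 5.4 says: "There are no follow-up procedures or therapy transitions". Section 7.2.1, item 2, puts reporting in the participant's hands: "Participants will be instructed to contact study staff if they noticed any of the symptoms listed above after participation in the study". It then allows, but does not require, staff to contact participants, and only about problems that arose during the experiment. Item 3 of the same section, which comes after that instruction, names the needle risks (hemorrhage, hoarseness, infection, swallowing difficulty) and adds: "Subjects may experience localized minor discomfort in the area during the procedure and for 1-2 days afterwards".

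Sections 7.2 and 7.4 also require continuous monitoring by staff, recording of all adverse events in the study period, and a causality assessment for each.

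**The concern.** Each participant has, in one visit, a lidocaine injection and needle insertion into the larynx, about 30 minutes of TMS testing, 1200 pulses of rTMS, and about 30 minutes of further TMS testing. There is no sham arm (section 5.3), so the timing of a symptom is one of the few aids to judging its cause. Staff who follow 5.5 or 7.2.1 will not collect the form that 7.2 requires right after rTMS, and the safety data will differ according to which section was followed.

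Section 7.4 still asks for a causality judgement on every event. An event whose cause is unknown and whose link to the device is doubtful is classed, for reporting, as device-associated. A poorly dated needle symptom could therefore be counted against the device.

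The second issue is what happens after the participant leaves. A result of no serious adverse events is only as good as the effort to find them, and the plan has no routine step that looks for events after the visit.

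**Working it through.** The plan states no figure on this point, so the main check sets the passages side by side.

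**Form schedule**

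| Point in the visit | 7.2 | 7.2.1 | 5.5 |
|---|---|---|---|
| Before TMS testing | yes | yes | yes |
| After electrode placement and pre-tests, just before rTMS | no | no | no |
| Right after rTMS | yes | no | no |
| End of the experiment | yes | yes | yes |
| Total | 3 | 2 | 2 |

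**What each version can date**

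- Two forms: one interval covers electrode placement, pre-tests, rTMS, post-tests and wire removal.
- Three forms: the first interval covers electrode placement, pre-tests and rTMS; the second covers the post-tests and wire removal. This separates events up to the end of rTMS from later ones. It does not separate rTMS from the steps before it.
- Three forms plus one just before rTMS: rTMS has an interval of its own.

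One assumption enters here. Section 5.5 does not list electrode placement. I place it after the first form and before the pre-tests, because the pre-tests record from the thyroarytenoid electrode. If the first form were completed after placement, the pre-tests would still share an interval with rTMS.

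**After the visit**

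- Scheduled contact: none (5.4).
- Participant-initiated reports: requested for the TMS symptoms named earlier in item 2. The needle risks come afterwards, in item 3.
- Staff-initiated contact: optional, and tied to problems arising during the experiment. An event that starts at home triggers nothing.
- End of the adverse event period for a participant: not defined in 7.4. Section 4.4.7 has participants exit on completing the protocol.

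**Illustration of size**

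Inputs: 40 planned participants, 20 per group (4.4.1), and a mild event rate of 5% (7.2.1). The 5% pools sham and real TMS sessions. It is neither an rTMS rate nor a delayed-event rate, so using it for delayed events is an assumption.

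- Expected participants with an event: 0.05 × 40 = 2.0.
- Chance that none is recorded, if a share s of events is captured: (1 − 0.05s)^40.

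| Assumed capture s | Chance of recording none in 40 |
|---|---|
| 100% | 0.95^40 = 0.13 |
| 75% | 0.9625^40 = 0.22 |
| 50% | 0.975^40 = 0.36 |
| 25% | 0.9875^40 = 0.60 |

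For serious adverse events, none in 40 gives a one-sided 95% upper bound of 1 − 0.05^(1/40) = 7.2%. None in one group of 20 gives 1 − 0.05^(1/20) = 13.9%. Both bounds presume that every event was ascertained.

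**The case against.** The strongest case on the other side is that this is a minor inconsistency and that little in the plan depends on it. Much of that case stands.

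- A reader might infer that the form is the only safety instrument. It is not. Section 7.2 provides for continuous monitoring, including feedback from subjects and observations by nurses and staff; 7.4.1 requires observed and volunteered effects to be recorded with enough detail to judge causality; and 7.2.2 puts a physician on site during electrode placement. Some events can be dated without the form.
- A reader might infer that the conflict between sections causes the attribution problem. It does not: the three-form version has the same gap before rTMS, and without a sham arm attribution stays limited however many forms are used.
- A reader might take an rTMS adverse event rate to be the primary safety result. The plan names none. Aim 1 rests on serious adverse events and completion, and the primary endpoint in 4.3.1 is corticospinal excitability.
- The one delayed effect given a duration is minor discomfort from the needle. It is anticipated and local, and missing it would not bias an rTMS event rate. The listed TMS effects and needle risks also differ in kind, which helps to tell them apart.
- The form and the experiment checklist are attachments (section 14) not available here. The form may ask for time of onset, and the checklist may be what staff actually follow.
- Section 7.5 classes the study as no more than minimal risk.

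These points limit the consequences, but they do not remove the conflict between sections or supply a planned look after the visit. Staff can observe and date events only while the participant is present.

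**Conclusion.** The point holds in three parts.

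1. Section 7.2 conflicts with 7.2.1 and 5.5, three forms against two. This is certain from the text.
2. No version has a form just before rTMS, so the forms alone cannot assign a new symptom to rTMS rather than to electrode placement or the pre-tests. This rests on the visit order assumed above and on the form not asking for time of onset.
3. Capture after the visit is passive, the reporting instruction omits the needle risks, and the adverse event period has no stated end. Mild and delayed events may be under-recorded, and so may a serious event that starts after the visit, which Aim 1 would count.

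The size cannot be fixed from the documents. With an assumed 5% delayed-event rate, the chance of seeing none in 40 rises from 0.13 at full capture to between 0.22 and 0.60 at assumed captures of 75% down to 25%.

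Stronger readings go too far. Delayed events are not simply missed, because participants are told to call. Aim 1 is not defeated, because a serious event or a non-completion during a supervised visit would be seen. Nor is it useful to argue that losing one of two expected events halves the estimate: that is true of any two events and says nothing about how likely a loss is. What remains is a worthwhile, inexpensive repair to the safety data of a first study of its kind.

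**What to change.** 1. Carry the post-rTMS form from 7.2 into 7.2.1 and 5.5, so that all three sections give the same schedule. Add electrode placement to the table in 5.5 so that the order of steps is explicit.
2. Add one short form after electrode placement and the TMS pre-tests, just before rTMS. In section 6.2, state that new symptoms will be tabulated by step and by group.
3. Extend the post-visit reporting instruction in 7.2.1 to the needle risks in item 3.
4. Replace the optional staff contact with one scheduled call or email to every participant after the 1-2 day period named in 7.2.1. Amend 5.4 to match, and state in 7.4 that this contact closes the adverse event window.

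Cost: one or two extra short forms per participant, depending on which section is now followed, and about 40 to 50 brief contacts. No extra visit or procedure is needed, and rTMS delivery is unchanged. Attribution will still be limited without a sham arm, and the report should say so.

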5.3 Clinical Procedures

Clinical assessment: Voice measures consisting of standard and published clinical scales will be collected for all participants to explore changes in voice quality (Zraick *et al.*, 2011; Samargia *et al.*, 2016). Voice quality will be measured by asking subjects to repeat 10 sentences with a high number of initial adductor phonemes, which often elicit symptoms in those with AdSD. These voice samples will be acquired digitally using a microphone. The frequency of voice breaks in the

recorded 10 sentences will be counted. These voice breaks will be the measure of disease severity. Other voice characteristics will be assessed using the Consensus Auditory-Perceptual Evaluation of Voice (CAPE-V) and the Voice Handicap Index (VHI). The CAPE-V is a reliable, valid clinical measure used by voice experts to assess voice quality. During a video recording, participants will be asked to repeat 6 sentences and then describe their voice problems. Voice experts will use the recording to rate voice quality based on several criteria (loudness, pitch, strain, breathiness, roughness, overall severity and others). In the current study, the total score in this scale will be used to rate the voice quality of participants before and after rTMS. The VHI is a self-administered questionnaire with questions about how often a given voice-related problem affects the life of participants. It reliably measures the influence of the subjects' voice disorder on their quality of life across three dimensions including: physical, functional and social. The total score for each participant will be measured before rTMS to assess how the voice disorder affects quality of life.

TMS testing: TMS testing will be performed to measure the corticospinal excitability before and after rTMS. TMS testing will be completed according to established methods (Kimberley and Di Fabio, 2010; Samargia *et al.*, 2014; Kimberley *et al.*, 2015a; Kimberley *et al.*, 2015b). Single and paired-pulse TMS testing will be delivered with a 70-mm figure-of-eight coil connected to a Magstim 200 stimulator (Magstim Company, Dyfed, UK), positioned on the scalp area over the left primary motor cortex. The laryngeal motor cortex will be identified by measuring the motor evoked potentials (MEP) of the thyroarytenoid muscle. Cortical stimulation will be spatially tracked with a neuronavigation system (BrainSight, Rogue Research Inc. Quebec, Canada) to decrease variability of stimulus delivery.

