The TMS variables that will be measured in the study include single pulses that evoke a response in the muscle. The variable of interest is the amplitude of motor evoked potential (MEP) in response to different stimulation intensities and duration of silent period after the evoked response. Testing will include no more than 200 pulses (rTMS delivery will involve 1200 pulses — see below). Overall, the testing procedures will take approximately 60 minutes (30 minutes before and 30 after rTMS).

Fine-wire electrodes: All participants will undergo vocal muscle testing using fine-wire EMG. With the subject seated in a supportive chair, fine-wire EMG electrodes will be inserted in the thyroarytenoid muscles (the "vocal cords") by a trained physician, [name]. The skin on the throat will be numbed using a lidocaine cream and also an injection of a lidocaine (numbing) agent. Once the skin has been numbed, the electrode will be placed into the muscle. To place the electrode, two fine wires will be inserted using a small gauge needle (30MM, 27 guage) with the edges of the wire electrode hooked around the tip of the needle and connected to an EMG machine. The needle will be passed through the skin and into the larynx. When the vocal cord is entered, an increased EMG signal associated with speech is detected. The needle will then be removed, leaving only the flexible wires in place.

Once the needle is removed, participants will not feel the presence of the electrode. Participants will be able to breath, talk and move their head with the electrode in place. At the end of the testing for vocal muscles, the electrodes will be gently pulled out. This process is nearly unnoticeable due to the very small diameter of the wires. Procedures will be the same as previous study (IRB # 0608M91226. Study Title "Pathophysiology of Spasmodic dysphonia: a TMS study").

rTMS application: rTMS will be delivered to the left laryngeal motor cortex with a hand-held figure-of-eight coil positioned over the scalp and connected to a Rapid² magnetic stimulator (Magstim Company, Dyfed, UK). The protocol described below is FDA approved and has been used extensively by our lab without incident. The risk of seizure is minimized by using a low rate of stimulation and a sub-threshold level of intensity.

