7.3 Anticipated Adverse Events

Risks associated with TMS are rare but should be recognized and prevented with appropriate precautions. Serious adverse risks include the induction of a seizure. Mild adverse effects include fainting, headache, dental pain, and other changes in memory, mood, and hearing. TMS delivery may also interfere with implanted devices.

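### The contact instruction, the symptom form's stated purpose and the anticipated-event list name TMS effects only, so delayed electrode harms are captured only if a participant happens to volunteer them

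*Combined protocol and SAP*

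**What the plan says.** The electrode procedure applies to everyone. Section 5.3 states: "All participants will undergo vocal muscle testing using fine-wire EMG". Section 4.4.1 plans 40 participants, 20 with AdSD and 20 healthy controls. Section 7.2.1 item 3 sets out the harms: "Risks associated with the electrode placement are very rare and include vocal cord hemorrhage, hoarseness of voice, infection, or dysphagia". It adds: "Subjects may experience localized minor discomfort in the area during the procedure and for 1-2 days afterwards".

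The texts that govern how harms are sought are these:

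- **Instruction for after the visit (7.2.1 item 2, on TMS):** "Participants will be instructed to contact study staff if they noticed any of the symptoms listed above after participation in the study".
- **Staff contact (same item):** "study staff may contact participants (via email or phone call) to follow-up on any issues or symptoms that occur during the experiment".
- **Purpose of the Subject Report of Symptoms (7.2):** "To monitor symptoms or changes in health status due to TMS testing and rTMS delivery".
- **Anticipated events (7.3):** the section opens with "Risks associated with TMS are rare but should be recognized and prevented with appropriate precautions" and goes on to list TMS effects only.

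Section 4.1 provides for a single session, and 5.4 says that there are no follow-up procedures. The first objective in the Study Summary is safety and feasibility of the protocol as a whole. Aim 1 in section 3.1 is worded for rTMS and is judged by the absence of serious adverse events and by 100% completion.

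**The concern.** The fine-wire electrodes are the only invasive part of the study, and the protocol itself names their harms. Some of these, such as infection or swallowing difficulty, may appear or be noticed only after the participant has gone home, and item 3 itself expects discomfort to outlast the visit. The wording that tells participants what to report, says what the form is for and lists what is anticipated was nevertheless written around TMS.

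What is at stake is how a result of no electrode events can be read. If such events are neither prompted nor listed, their absence from the safety table may mean that none occurred or that nobody mentioned them. This bears most directly on the Study Summary objective, which covers the whole procedure. It bears on Aim 1 only through a serious event that arises later and is never volunteered.

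**Working it through.** The plan has no figure to reproduce here. Section 4.4.1 says there were no data for a sample size calculation, and item 3 gives no event rate beyond calling the risks very rare. The check is therefore mainly a comparison of texts.

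1. **Order within 7.2.1.** Item 1 concerns confidentiality, item 2 TMS and item 3 the electrodes. The contact instruction sits in item 2 and points upward. The symptoms above it are seizure, mania, fainting, headache, dental pain, and changes in memory, mood and hearing. Electrode harms included: 0 of 4.
2. **Section 7.3.** It lists seizure, fainting, headache, dental pain, changes in memory, mood and hearing, and interference with implanted devices. Electrode harms included: 0 of 4.
3. **Form purpose in 7.2.** It names TMS testing and rTMS delivery; electrode placement is not mentioned. Item 2 of 7.2.1 describes the same form more widely, as a way to act on any change in health.
4. **Timing of the form.** Section 7.2 gives three completions; 7.2.1 item 2 and the schedule in 5.5 give two. All three places put the last completion at the end of the visit, so the form cannot pick up a later harm, whatever its items are.
5. **Staff contact.** This is optional and is tied to problems arising during the experiment. It is not restricted to TMS symptoms, so an electrode symptom that starts at the visit is within its scope. One that starts later is not.
6. **Recording rule in 7.4.1.** It covers effects that are seen or reported, whatever the suspected cause. After the visit staff see nothing, so only the participant's report remains, and the instruction on what to report omits these harms.

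**What incomplete capture does to a zero count (illustration).** With no events reported among n participants and full capture, the exact one-sided 95% upper bound on the event rate is U = 1 − 0.05^(1/n). For n = 40, U = 1 − 0.05^(1/40) = 7.2%. If only a share s of events is captured, the reported rate is s times the true rate, so the bound on the true rate is U/s:

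- s = 0.75: 7.2158% / 0.75 = 9.6%
- s = 0.50: 7.2158% / 0.50 = 14.4%
- s = 0.25: 7.2158% / 0.25 = 28.9%

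The documents give no value for s; these are assumptions that show direction and scale only.

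**The case against.** Much of the case on the other side is sound.

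- **The harms may be solicited after all.** The symptom form, both consent forms and the experiment checklist are attachments whose content is not available here, and item 2 says that the form serves to catch any change in health. A reader might infer that electrode harms are never asked about; the documents do not show that. They support only the narrower statement that the visible text documents no such solicitation.
- **Adverse event rules are broad.** The definition in 7.1 covers any symptom, 7.4.1 records effects regardless of cause, staff monitor participant feedback continuously, and a physician is on site during electrode placement. This stands for the visit itself. It classifies events and deals with those that come to light, but it does not prompt a report from home.
- **Aim 1 would hardly move.** A reader might infer that Aim 1 could wrongly declare the electrode procedure safe. Its criterion counts serious events and completion, so hoarseness or local discomfort would leave it unchanged even if fully reported, unless a participant failed to complete.
- **Regulatory reporting is not in doubt.** A reader might infer that the omission from 7.3 makes a serious electrode event unexpected and so alters its reporting route. The device-effect definition in 7.1 turns on whether the effect was identified in the investigational plan, and 7.2.1 identifies all four harms. Under 7.4.2, serious events that are at least possibly related are reported without an expectedness test.
- **Voice ratings do not fill the gap.** Section 5.3 says of the CAPE-V: "In the current study, the total score in this scale will be used to rate the voice quality of participants before and after rTMS". A reader might infer that electrode hoarseness will be absorbed into that outcome, or that its roughness and breathiness ratings could serve as a safety measure. Neither follows. Observed adverse effects must be recorded anyway, and a same-visit change may mix electrode, lidocaine, rTMS and disease effects and cannot detect later harm.
- **A probability of at least one electrode event in 40 would not help.** It would need an invented rate, and it would describe how often events occur, not how often they are missed.

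What survives is the mismatch between item 3 and the three texts, and its effect on harms that arise after the visit.

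**Conclusion.** The point holds in a limited form. Sections 7.2, 7.2.1 item 2 and 7.3 are not aligned with 7.2.1 item 3: the instruction's symptoms and the 7.3 list include 0 of the 4 named electrode harms, and the form's purpose in 7.2 omits electrode placement. All 40 planned participants are exposed. After the single visit, capture rests on unprompted reports.

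The consequence is a weaker no-events statement for the Study Summary objective and the possibility that a delayed serious electrode event escapes Aim 1. How much is lost cannot be estimated, because neither the event rate nor the capture share is given.

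The conclusion assumes that the attached form and participant materials do not already extend the instruction to electrode harms. If they do, what remains is a consistency edit to the protocol. Either way this is a cheap improvement and not a flaw that undermines the study.

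**What to change.** Reconcile 7.2, 7.2.1 item 2 and 7.3 with 7.2.1 item 3, so that the contact instruction, the form's stated scope and the anticipated-event list all include the harms that the protocol already names for the electrodes. If the attached form and participant materials already do this, say so and cite them in 7.2. While those sentences are open, also reconcile the number of form completions (three in 7.2; two in 7.2.1 item 2 and 5.5).

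In the descriptive safety summary, report electrode-attributed and TMS/rTMS-attributed events in separate rows, by group, so that an absence of events can be read for each procedure.

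The cost is a short amendment, possibly an edit to the form and participant instruction, and one additional split in a table. No visit, call or staff is added. The downside is that a few more minor events will probably be reported, so the safety table will look slightly less favourable.
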